3 STUDY OBJECTIVES AND ENDPOINTS

3.1 Objectives

The primary objective of this study is to evaluate the long-term safety, tolerability, and efficacy of ABBV-105 and ABBV-599 in RA subjects who have completed Study M16-063.

3.2 Efficacy Endpoints

There is no primary efficacy endpoint since this is the extension to the feeder Study M16-063. Efficacy endpoints for this study, measured at each study visit, include the following:

- Change in disease activity score (DAS)28 (C-reactive protein [CRP]) from baseline of Study M16-063;
- Proportion of subjects achieving DAS Low Disease Activity (LDA), defined as DAS28 CRP ≤ 3.2 ;
- Proportion of subjects achieving DAS Clinical Remission (CR), defined as DAS28 CRP < 2.6 ;
- Change in clinical disease activity index (CDAI) from baseline of Study M16-063;
- Proportion of subjects achieving LDA based on CDAI criteria, defined as CDAI ≤ 10 ;
- Proportion of subjects achieving CR based on CDAI criteria, defined as CDAI ≤ 2.8 ;
- Proportion of subjects achieving American College of Rheumatology (ACR) 20/50/70 response. A subject will be considered an ACR 20/50/70 responder if:
 - The swollen joint count (SJC) and tender joint count (TJC) have decreased from baseline of Study M16-063 by 20/50/70% or more.
 - At least 3 of the 5 remaining ACR core set measures (i.e., Patient's Assessment of Pain [using visual analog scale, VAS], Patient Global Assessment of Disease Activity [PtGA], Physician Global Assessment of Disease Activity [PhGA], Health Assessment Questionnaire Disability Index [HAQ-DI], and high-sensitivity C-reactive protein [hsCRP]) show reduction of 20/50/70% or more from baseline of Study M16-063.
- Change in individual components of ACR from baseline of Study M16-063, to include:
 - SJC,
 - TJC,

- Patient's Assessment of Pain (using VAS),
 - PtGA,
 - PhGA,
 - HAQ-DI, and
 - hsCRP.
- Change in Morning Stiffness from baseline of Study M16-063.

3.3 Safety Endpoints

Safety evaluations include AE monitoring, physical examinations, vital sign measurements, electrocardiogram (ECG), and clinical laboratory testing (hematology, chemistry, and urinalysis) as a measure of safety and tolerability for the entire study duration.

An internal data monitoring committee (DMC) will review unblinded safety data on a cohort level throughout the course of the study. A separate DMC charter has been prepared outside of the protocol and describes the roles and responsibilities of the DMC members, frequency of data reviews, relevant safety data to be assessed, and expectations for blinded communications.

The DMC will be responsible for safeguarding the interests of trial subjects by assessing the safety and, if appropriate, the efficacy data of the interventions during the trial, as well as for monitoring the quality and integrity of the clinical trial. The DMC will provide recommendations to the AbbVie contact about stopping, modifying or continuing the trial without modification. The DMC may also formulate recommendations relating to the selection/recruitment/retention of subjects, their management, improving adherence to protocol-specified regimens and retention of subjects, and the procedures for data management and quality control.

The DMC is a multidisciplinary group consisting of clinicians and biostatisticians who, collectively, has knowledge in the management of patients with rheumatoid arthritis (RA) and experience in the conduct and monitoring of randomized clinical trials. The DMC reviews the available safety data, and as applicable, the critical efficacy endpoints, assessing risks and benefits, and recommends to the AbbVie Contact whether to continue without change, modify, or stop the Study M16-063 clinical trial.

All DMC members will be internal AbbVie members with expertise in clinical safety monitoring and who have no affiliation with ABBV-599. Following initiation of the study, DMC members will have no involvement in the conduct of Study M16-063 or other ABBV-599 clinical trials outside their role on the DMC. All DMC members have agreed to not discuss unblinded data with those who have involvement with Study M16-063 or ABBV-599 development until the Study M16-063 unblinded information is made available to the team.

An independent Cardiovascular Adjudication Committee (CAC) will adjudicate blinded cardiac and cerebrovascular events. A CAC charter has been prepared separately from the protocol and defines objective, scope, frequency, and triggers of data reviews.

The clinical trial is to be discontinued or terminated in case of an unacceptable risk, relevant toxicity, or a negative change in the risk/benefit assessment. This might include the occurrence of adverse events

of which character, severity or frequency is new in comparison to the existing risk profile. In addition any data deriving from other clinical trials or toxicological studies which negatively influence the risk/benefit assessment might cause discontinuation or termination of the study.

3.4 Biomarker Research

Optional samples (whole blood, serum, and plasma) will be collected at specific time points as described in the Activity Schedule ([Appendix D](#)) to evaluate known and or novel disease related or drug related biomarkers. Types of biomarkers may include nucleic acids, proteins, lipids, and/or metabolites. The objective of research is to analyze samples for biomarkers that will help to understand RA, related conditions, and response to treatment with ABBV-105 and upadacitinib or similar compounds. Research on samples collected in Germany will be limited to RA, ABBV-105, and upadacitinib. Research may also include changes in epigenetics, gene expression, and proteomics that may be associated with RA, related conditions, or the subject's response to treatment. This research is exploratory in nature, and the results may not be included with the clinical study report.

4 INVESTIGATIONAL PLAN

4.1 Overall Study Design and Plan

This is a Phase 2, double-blind, multicenter, long-term extension (LTE) study to assess the safety, tolerability, and efficacy of ABBV-105 and ABBV-599 in RA subjects who have completed Study M16-063. Subjects who meet eligibility criteria (Section 5.1) and enter the study on ABBV-105, ABBV-599, or upadacitinib from Study M16-063 will continue on their previously-assigned treatment through the end of the LTE study. Subjects who meet eligibility criteria and enter the study on placebo for both ABBV-105 and upadacitinib from Study M16-063 will receive ABBV-599. Study drug treatment assignments include the following:

[figure not shown]
- Group 1: ABBV-599 (ABBV-105 60 mg and upadacitinib 15 mg) administered once a day (QD),
- Group 2: ABBV-105 60 mg and upadacitinib placebo QD,
- Group 3: ABBV-105 20 mg and upadacitinib placebo QD
- Group 4: ABBV-105 5 mg and upadacitinib placebo QD, and
- Group 5: Upadacitinib 15 mg and ABBV-105 placebo QD.

This study plans to enroll subjects who completed Study M16-063 at approximately 39 sites in Canada and the European Union. The number, allocation, and location of sites may vary depending on operational aspects of the study. Study sites and subjects will remain blinded for the duration of the study.

The duration of the LTE study will be approximately 52 weeks. This includes a 48-week double-blind treatment period with study visits conducted at Weeks 18, 24, 30, 36, 48, and 60 from the baseline visit of Study M16-063. In addition, subjects will also have a telephone follow-up call 30 days after their last visit to determine the status of any ongoing AEs/SAEs or the occurrence of any new AEs/SAEs.

The schematic of the study is shown in Figure 1. Further details regarding study procedures are located in the Operations Manual.

Figure 1. Period 1 Schematic

QD = administered once a day

4.2 Discussion of Study Design

Choice of Control Group

Subjects will roll over from Study M16-063 and continue on their originally randomized treatment, with the exception of those originally randomized to placebo, who will roll over to ABBV-599. The objective of this LTE study is to evaluate long term safety and efficacy of ABBV-105 and ABBV-599, and thus primary comparison will be relative to the safety and efficacy profile observed in each arm during the initial randomized study.

Appropriateness of Measurements

Standard statistical, clinical, and laboratory procedures will be utilized in this study. All efficacy measurements in this study are standard for assessing disease activity in subjects with RA. All clinical and laboratory procedures in this study are standard and generally accepted.

Suitability of Subject Population

This LTE study will enroll subjects who have completed Study M16-063. Only those subjects who have met all of the specified eligibility criteria will have an option to enter into the LTE study to receive

continued therapy, provided the subject is willing and the investigator believes that continuing therapy is appropriate.

Selection of Doses in the Study

Since the study is a continuation of the initial Phase 2 dose exploration study of ABBV-105 and ABBV-599, the doses selected for this study are the same as those used previously in Study M16-063. These doses were determined based on an analysis of pharmacokinetic, pharmacodynamic, and safety data from Phase 1 studies in healthy volunteers for ABBV-105 and Phase 2 and Phase 3 studies for upadacitinib, in addition to efficacy data for upadacitinib in RA.

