7.3 Statistical Analyses for Efficacy

Analysis of efficacy endpoints will be conducted on the FAS based on treatments as randomized for Study M16-063. The analysis will be based on As Observed data, and no imputation will be conducted. The analysis treatment groups will be described as follows indicating from Study M16-063 to extension Study M16-763:

- Group 1: ABBV-599 to ABBV-599
- Group 2: ABBV-105 60 to 105 60 mg
- Group 3: ABBV-105 20 to 105 20 mg
- Group 4: ABBV-105 5 to 105 5 mg
- Group 5: Upadacitinib 15 to Upadacitinib 15 mg, and
- Group 6: Placebo to ABBV-599
- Group 7: All ABBV-599 (Group 1 and 6)

The baseline for all efficacy analyses in this study will be the baseline in Study M16-063.

There is no primary efficacy endpoint and no formal statistical tests will be applied. Only descriptive statistics will be used for all efficacy endpoints. Descriptive statistics will be provided for each treatment group for all visits. These include the number of observations, mean with 95% confidence interval, standard deviation, median, minimum and maximum for continuous endpoints (or the change from baseline measurements), and frequencies and percentages with 95% confidence interval for binary endpoints.

No missing data imputation will be applied. All efficacy analyses will be based on As Observed analysis, and thus a subject who does not have an evaluation at the primary analysis time point will not be included.

Details on efficacy analyses are provided in the SAP.

Sample Size Estimation

This is the LTE study for Study M16-063. All eligible subjects who completed Study M16-063 will be enrolled in this study if the subject signs and dates the informed consent. Based on discontinuation criteria mandating efficacy, it is estimated that 20 - 60% of subjects (i.e., between 40 and 120 subjects) will ultimately complete the LTE.

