#### **Clinical Hypothesis**

[figure not shown]
The safety and efficacy of ABBV-105 and ABBV-599 will be maintained over an extended period of treatment.

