### **3.2 Secondary Efficacy Endpoints**

1. Change in disease activity score (DAS)28 (C-reactive protein [CRP]) from baseline of Study M16-063;
2. DAS Low Disease Activity (LDA), defined as DAS28 CRP  $\leq$  3.2;

3. DAS Clinical Remission (CR), defined as DAS28 CRP < 2.6;
4. Change in clinical disease activity index (CDAI) from baseline of Study M16-063;
5. LDA based on CDAI criteria, defined as CDAI  $\leq$  10;
6. CR based on CDAI criteria, defined as CR  $\leq$  2.8;
7. American College of Rheumatology (ACR) 20/50/70 response. A subject will be considered an ACR 20/50/70 responder if:
  - The swollen joint count (SJC) and tender joint count (TJC) have decreased from baseline of Study M16-063 by 20/50/70% or more.
  - At least 3 of the 5 remaining ACR core set measures show reduction of 20/50/70% or more from baseline of Study M16-063.
    - Patient's Assessment of Pain [using visual analog scale, VAS],
    - Patient Global Assessment of Disease Activity [PtGA],
    - Physician Global Assessment of Disease Activity [PhGA],
    - Health Assessment Questionnaire Disability Index [HAQ-DI]
    - High-sensitivity C-reactive protein [hsCRP])
8. Change in individual components of ACR from baseline of Study M16-063, to include:
  - SJC,
  - TJC,
  - Patient's Assessment of Pain (using VAS),
  - PtGA,
  - PhGA,
  - HAQ-DI, and
  - hsCRP.
9. Change in Morning Stiffness Severity (11 point scale) from baseline of Study M16-063.

10. Change in Morning Stiffness Duration (Hours and Minutes) from baseline of Study M16-063

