## **8.4 Secondary Efficacy Analyses**

Descriptive statistics will be provided for each treatment group for all visits. These include the number of observations, mean with 95% confidence interval, standard deviation, median, minimum and maximum for continuous endpoints; and frequencies and percentages with 95% confidence interval using Wilson score for binary endpoints.

No missing data imputation will be applied. All efficacy analyses will be based on As Observed (AO) analysis, and thus a subject who does not have an evaluation at the primary analysis time point will not be included.

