### **9.2 Adverse Events**

Adverse events (AEs) will be summarized and presented using primary MedDRA System Organ Classes (SOCs) and preferred terms (PTs) according to the version of the MedDRA coding dictionary used for the study at the time of database lock. The actual version of the MedDRA coding dictionary used will be noted in the AE tables and in the clinical study report. Specific adverse events will be counted once for each subject for calculating percentages, unless stated otherwise. In addition, if the same adverse event occurs multiple times within a subject, the highest severity and level of relationship to investigational product will be reported.

TEAEs will be summarized using subject data from Study M16-763 and a combination of data from Studies M16-063 and M16-763 that includes any subject receiving a dose in Study M16-763, respectively. Only the datasets from Studies M16-063 and M16-763 that includes any subject receiving a dose in Study M16-763 will be used for per 100 patient years of exposure analyses (for the Study M16-763 study).

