## **12.0 Overall Type-I Error Control**

No hypothesis tests will be conducted for the efficacy analysis.

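### The primary comparison named in Protocol 4.2, each arm against its own M16-063 profile, is not computed by any SAP analysis, and a change in event rate between the two periods cannot be seen

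*Protocol*

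**What the plan says.** Protocol 4.2 (Choice of Control Group) states that the "primary comparison will be relative to the safety and efficacy profile observed in each arm during the initial randomized study". The clinical hypothesis, given in both documents, is one of maintenance: "The safety and efficacy of ABBV-105 and ABBV-599 will be maintained over an extended period of treatment". No criterion or margin for maintenance is given, and SAP 12.0 adds "No hypothesis tests will be conducted for the efficacy analysis".

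On efficacy, Protocol 7.3 fixes the reference point: "The baseline for all efficacy analyses in this study will be the baseline in Study M16-063". SAP 8.4 then says "Descriptive statistics will be provided for each treatment group for all visits". The data are As Observed, "thus a subject who does not have an evaluation at the primary analysis time point will not be included". The endpoints in SAP 3.2 are changes from the M16-063 baseline, ACR response relative to that baseline, and status measures such as "DAS Clinical Remission (CR), defined as DAS28 CRP < 2.6". SAP 8.5 and 10.0 plan nothing further.

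On safety, SAP 9.2 summarises treatment-emergent adverse events (TEAEs) for M16-763 alone and for the two studies combined. Only the combined data of subjects dosed in M16-763 "will be used for per 100 patient years of exposure analyses", and SAP 9.2.4 defines the rate over both studies. SAP 9.3 tabulates mean laboratory changes at the visits of both studies.

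**The concern.** The question the study sets itself is whether what was seen in the first 12 weeks holds up over the next 48. Answering it needs two things side by side in each arm: the M16-063 result and the M16-763 result, on the same scale and, for efficacy, in the same subjects. The SAP does not define that pairing. The contrasts it does compute are between treatments: differences in percentages for adverse events of special interest (SAP 9.2.2), and ANOVA on laboratory and vital sign changes (SAP 9.3 and 9.4).

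Two wrong conclusions become possible. A rise in the event rate during the extension could be partly averaged away by the first 12 weeks, or a fall could go unseen. And a Week 60 response proportion that looks as good as or better than Week 12 could reflect who was still being observed rather than any maintained benefit.

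**Working it through.** **1. The plan's own figure.** Protocol 7.3 and SAP 2.4 expect 20–60% of subjects, 40 to 120, to complete. 40 / 0.20 = 200 and 120 / 0.60 = 200, so both ends imply 200 entrants, a number that is never stated. The figure reproduces. It is the only numeric design figure, and it counts completers, not subjects observed at Week 60.

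**2. What the SAP provides for each part of the comparison.**

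| Quantity | M16-063 period alone | M16-763 period alone | Contrast between periods |
|---|---|---|---|
| Efficacy by visit | Not stated whether Week 12 is among the visits shown | Yes, As Observed | None |
| TEAE numbers and percentages | No | Yes | None |
| TEAEs per 100 patient-years | No | No (combined only) | None |
| Laboratory mean change | Yes | Yes | None (ANOVA is between arms) |

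The M16-763 percentages do not fill the gap. Percentages collected over 12 weeks and over up to 48 weeks are not comparable without adjusting for exposure.

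**3. What the pooled rate can and cannot show.** Let s be the M16-063 share of exposure, r1 the rate in M16-063 and r2 the rate in M16-763. Then pooled rate = s × r1 + (1 − s) × r2. M16-063 is taken as 12 weeks (84 days, from the LTE Baseline/Week 12 visit) and M16-763 as 48 weeks (336 days). The rates are assumed for illustration.

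- Subject completing both studies: s = 84 / 420 = 0.20. A doubling from 10 to 20 gives 0.20 × 10 + 0.80 × 20 = 18.0.
- Only 24 extension weeks: s = 12 / 36 = 0.33, pooled 16.7.
- Only 12 extension weeks: s = 12 / 24 = 0.50, pooled 15.0.

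With s = 0.20, a pooled rate of 20 arises from each of these:

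- no change: 0.20 × 20 + 0.80 × 20 = 20
- a fall: 0.20 × 40 + 0.80 × 15 = 20
- a rise: 0.20 × 10 + 0.80 × 22.5 = 20

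**4. How far by-visit efficacy could drift.** Assume 200 entrants, 100 in LDA at Week 12 (50%), nobody changing state, and 80 non-LDA subjects not observed at Week 60. Observed LDA is 100 / 120 = 83%. With 60 in LDA at Week 12 (30%) and the same 80 unobserved, it is 60 / 120 = 50%. Neither rise reflects improvement. If the unobserved subjects were a random sample, the proportion would stay at its Week 12 value. These are bounds under assumed inputs, not estimates.

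**5. Group 6.** These subjects took placebo in M16-063 and ABBV-599 in M16-763 (SAP 8.1). Their M16-063 profile is a placebo profile. The combined exposure formula in SAP 6.0 runs from the first M16-063 dose, so it spans placebo time. SAP 6.0 lists a placebo exposure group, which suggests a split, but gives no rule for it.

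**The case against.** The strongest reply is that Protocol 4.2 gives design rationale, not an analysis instruction, and that the operative sections promise only descriptive statistics with no primary efficacy endpoint. M16-063 also has its own Week 12 lock and analysis, whose outputs are not visible here, and the common baseline puts efficacy changes from both studies on one scale. It stands that no formal test is owed. But a descriptive comparison still has to be defined, and none is. A separate M16-063 report cannot close the gap on event rates, because this SAP produces no M16-763-only rate to set beside it. The combined set also excludes anyone not dosed in M16-763, so it is not the profile observed in each randomised arm.

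Several stronger readings are tempting and are not supported:

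- A reader might infer that efficacy is reported only as change from the M16-063 baseline. LDA and remission are status proportions, and the visits shown might include Week 12, though the SAP does not say so.
- A reader might infer that extension adverse events are reported only in pooled form. That is true of rates per 100 patient-years, but numbers and percentages are also given for M16-763 alone.
- A reader might infer that subjects lacking efficacy must drop out of the data. Protocol 5.6 asks that subjects who stop drug keep attending visits. The direction to discontinue in Protocol 5.5 rests on joint counts (no 20% improvement, or worsening at two consecutive visits), not on LDA. Missing the CDAI threshold leads to background adjustment and, from Week 24, to discontinuation being considered at the clinician's discretion. Drift therefore depends on how many subjects actually go unobserved. Those who stay add off-drug values, for which the SAP states no separate handling, so a clean maintenance reading is not available either way.
- A reader might carry the LDA example to 20% completion and infer 100% LDA because only non-LDA subjects leave. With 160 leavers and only 100 non-LDA subjects, at least 60 leavers would have to be in LDA, so the premise fails.

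**Conclusion.** The point holds in this limited form. The protocol names a primary comparison for which the SAP defines no analysis. The safety side is the firmer half: under the plan as written, no output gives an event rate per 100 patient-years for either period alone, so neither a change nor its direction can be read. With assumed rates, a doubling from 10 to 20 would appear as 18.0, 16.7 or 15.0 depending on whether extension exposure is 48, 24 or 12 weeks.

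On efficacy, the missing piece is a within-subject contrast with Week 12. Without it, By-visit As Observed figures can mislead to an extent that depends on follow-up after stopping drug, which the documents do not quantify; 83% against a true 50% is a bound under the stated assumptions. The documents do not support saying that the extension results will in fact be biased, or in which direction event rates will move. Since the study is descriptive and the data are already collected, this should be corrected, but it does not undermine the design.

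**What to change.** 1. **SAP 9.2 and 9.2.4.** Report events per 100 patient-years separately for the M16-063 period and the M16-763 period, by group, beside the combined rate. SAP 6.0 and 9.2.1 already define exposure and TEAEs for M16-763 alone. Keep Group 6 placebo exposure, and events arising in it, apart from its ABBV-599 exposure.
2. **SAP 8.4, Groups 1 to 5.** Name Week 12 as the reference for maintenance. Add the paired change from Week 12 to each extension visit, with 95% CI, in subjects observed at both. Add the share of Week 12 responders still responding, shown As Observed. As a labelled supplement, show it with the full Week 12 responder cohort as denominator, stating that this counts missing as non-response and so departs from the no-imputation rule.
3. **Group 6.** Present it separately. Its Week 12 value is a placebo result, and its later change measures a switch of treatment, not maintenance.

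If the sponsor does not intend the comparison, the alternative is to amend the sentence in Protocol 4.2 so that it matches the SAP.

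The cost is a few more descriptive tables from data already in the activity schedule or carried over from M16-063. The maintenance figures may look less favourable than the by-visit ones.
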